4.2.10 Exploratory Objective 5, Change from baseline in eGFR

4.2.10.1 Definition

Estimand is defined in section 4.2.

4.2.10.2 Derivations

See section 3.3.1.6. Data for calculation of eGFR1 should be collected for all post-randomization visits while data for calculation of eGFR2 will be collected at certain visits post-randomization, see CSP SoA for details.

4.2.10.3 Handling of Dropouts and Missing Data

No imputation will be done.

4.2.10.4 Primary Analysis of Exploratory objective

The analysis is performed using MMRM, similar to key objectives, for absolute change from baseline. Data will be summarised descriptively by treatment group and visit.

4.2.10.5 Additional Analyses of the Exploratory objective

Not applicable.

4.2.10.6 Subgroup Analyses

Not applicable.

4.2.11 Exploratory Objective 6, Change in PROs

4.2.11.1 Definition

Following data will be analysed:

CLDQ

- CLDQ Fatigue Symptoms score
- CLDQ Abdominal Symptoms score
- CLDQ Systemic Symptoms score
- CLDQ Activity Symptoms score
- CLDQ Emotion Symptoms score
- CLDQ Worry Symptoms score
- Total CLDQ score

SF-36v2 domain scores

- SF-36v2 Physical functioning score
- SF-36v2 Mental health score
- SF-36v2 Bodily pain score

- SF-36v2 General health score
- SF-36v2 Vitality score
- SF-36v2 Social Functioning score
- SF-36v2 Role limitations due to emotional problems score
- SF-36v2 Role limitations due to physical health score

SF-36v2 component scores

- SF-36v2 Physical Component Summary score
- SF-36v2 Mental Component Summary score

PGIS

- Patient Global Impression of Severity - Liver Disease (PGIS - Liver Disease)

Estimand is defined in section 4.2.

4.2.11.2 Derivations

SF-36v2

SF-36v2 will be scored by Quality Metric using norm-based scoring.

CLDQ

The CLDQ is comprised of six domains. The domains are listed below with the corresponding question numbers. First, the sum of the corresponding questions is taken. This is then divided by the number of items in the domain to get the domain score. To get the overall CLDQ score, the sum of the domains are taken and then divided by the total number of domains.

If items are missing the denominator below will need to be adjusted to match the number of items. If half or more of the items are missing it will not be calculated.

Abdominal (AB) = Sum of N1 + N5 + N17

Fatigue (FA) = Sum of N2 + N4 + N8 + N11+ N13

Systemic (SY) = Sum of N3 + N6 + N21 + N23 + N27

Activity (AC) = Sum of N7 + N9 + N14

Emotion (EM) = Sum of N10 + N12 + N15 + N16 + N19 + N20 + N24 + N26

Worry (WO) = Sum of N18 + N22 + N25 + N28 + N29

Each CLDQ domain symptoms score is calculated as:

ABM = AB/3

FAM = FA/5

SYM = SY/5

ACM = AC/3

EMM = EM/8
WOM= WO/5
CLDQM = SUM (OF ABM FAM SYM ACM EMM WOM)/6

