8.2.2.4 Patient-reported Outcomes

Patient-reported outcomes (PROs) refer to all symptoms, impacts, and outcomes that are directly reported by the participant. PROs have become important endpoints for regulatory and reimbursement authorities when evaluating efficacy or safety of treatment in clinical trials.

The following PROs will be administered in this study at the timepoints specified in the SoA (Table 1):

- Chronic Liver Disease Questionnaire (CLDQ)
- SF-36v2 acute
- Patient Global Impression of Severity - Liver Disease (PGIS - Liver Disease)

Participants will be asked to complete the questionnaires on a provisioned handheld electronic device. Paper questionnaires may be used if a provisioned handheld electronic device is not available or the participant is unable to use one.

The handheld device has been programmed to allow flexibility for participants to complete PRO questionnaires prior to the Visit 6 in-clinic visit. In case the PRO questionnaires are not completed before the in-clinic Visit 6, the participant should complete PROs at the site prior to other Visit 6 study procedures.

The following best practice guidelines should be followed:

- PRO questionnaires should be completed before any other study procedures during Visit 6, to avoid bias when responding to questions.
- Site personnel must show participants how to use the electronic PRO device, in accordance with the instructions provided.
- Participants must not receive help from relatives, friends, or site staff to answer or to clarify PRO questions.
- If participants have any medical problems, they should discuss them with their doctor or research nurse separately from the PRO assessment.
- Site staff must remind participants there are no right or wrong answers, and that the value and relevance of PRO data are to hear directly from participants, without interpretation from anyone else, how they function and feel.

CLDQ:

The CLDQ is a disease-specific PRO instrument, assessing symptoms and health-related quality of life, relevant for patients with liver disease. The CLDQ includes 29 items with a recall period of the past 2 weeks. The CLDQ includes 6 domains: Abdominal symptoms (3 items), Fatigue (5 items), Systemic symptoms (5 items), Activity (3 items), Emotional function (8 items), Worry (5 items). Scoring of this instrument produces a global score, as well as scores for each of the domains.

SF-36v2:

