4.2.11.3 Handling of Dropouts and Missing Data

No imputation will be done.

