4.2.11.4 Primary Analysis of Exploratory objective

Data will be descriptive summarized for each treatment group. PGIS will be presented with number and percentage per response category and timepoint, as well as shift from baseline. For the CLDQ and SF-36v2 actual score and change from baseline will be summarised for the different components.

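### The CLDQ total is divided by a fixed six with no rule for an uncalculated domain; run as written, it can come out at five-sixths of the mean of the available domains

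*SAP*

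**What the plan says.** SAP section 4.2.11.2 sets out the CLDQ scoring. It states "The CLDQ is comprised of six domains" and gives each domain score as the sum of its items divided by the number of items. For the total, the rule in words is that "the sum of the domains are taken and then divided by the total number of domains". The formula is "CLDQM = SUM (OF ABM FAM SYM ACM EMM WOM)/6".

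Two sentences ahead of the formulas deal with missing answers. The first concerns the divisors: "If items are missing the denominator below will need to be adjusted to match the number of items". The second sets the point at which a score is no longer produced, without naming which score is meant: "If half or more of the items are missing it will not be calculated".

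Section 4.2.11.3 then says "No imputation will be done".

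Protocol section 8.2.2.4 gives the item counts as "Abdominal symptoms (3 items), Fatigue (5 items), Systemic symptoms (5 items), Activity (3 items), Emotional function (8 items), Worry (5 items"). It makes the handheld device the usual mode of completion and allows paper as a fallback.

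The total CLDQ score is a named endpoint of the PRO objective in Protocol section 3 and of exploratory objective 6 in SAP Table 7. The Schedule of Activities has it collected at Visits 2 and 6 only. SAP section 4.2.11.4 says of its use: "For the CLDQ and SF-36v2 actual score and change from baseline will be summarised for the different components".

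**The concern.** The SAP foresees that a domain may go uncalculated, but both statements of the total keep six as the divisor. The denominator adjustment refers to items. That fits the domain divisors (3, 5, 5, 3, 8, 5) but not the six, which counts domains. A programmer who codes the line literally, in a language where a list-type SUM skips missing arguments, would add five domain means and divide by six.

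With only two assessments, an error at either one passes directly into the change score. Abdominal symptoms and Activity have three items each, so two skipped answers are enough to lose either domain. At stake is a wrong individual value, and a slightly wrong arm mean, for a named exploratory endpoint.

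**Working it through.** **Inputs from the documents.** Six domains with 3, 5, 5, 3, 8 and 5 items; a total divisor of 6; a score not calculated when half or more of its items are missing; no imputation; two assessments; 22 participants planned per arm (Protocol section 9.2).

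**Inputs assumed.** The documents give neither the CLDQ response scale nor its direction. A common domain mean *m* from 3 to 6 is used for illustration. SUM is taken to add only the available domains; the SAP does not state this.

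**1. Complete data.** 3 + 5 + 5 + 3 + 8 + 5 = 29 items, matching the protocol. With all six domains present, the sum divided by 6 is the mean of the domain means. The formula is correct when nothing is missing.

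**2. When a domain is lost.** Half or more missing means 2 of 3 items, 3 of 5, or 4 of 8.

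**3. Total with *k* domains missing.** Let A be the mean of the available domains. The formula returns (6 − k) × A / 6.
- k = 1: 5A/6, which is 16.7% below A.
- k = 2: 4A/6, which is 33.3% below A.

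The same result follows from entering zero for each missing domain and dividing by six.

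**4. Shortfall in points, one domain missing, all domain means equal to *m*.** m − 5m/6 = m/6.

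| *m* (assumed) | Sum/6 | Sum/5 | Shortfall |
|---|---|---|---|
| 3 | 2.50 | 3.00 | 0.50 |
| 5 | 4.17 | 5.00 | 0.83 |
| 6 | 5.00 | 6.00 | 1.00 |

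**5. Unequal domain means.** Take assumed means of 5.5, 4, 5, 5.2, 4.8 and 4.5, which sum to 29.0, so the true six-domain mean is 29.0/6 = 4.83.
- Losing the domain at 5.5 gives 23.5/6 = 3.92, which is 19.0% below 4.83.
- Losing the domain at 4 gives 25.0/6 = 4.17, which is 13.8% below.

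One-sixth is therefore exact against the mean of the available domains and only approximate against the six-domain mean.

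**6. Effect on change from baseline, stable participant, m = 5.**
- Missing at Week 6 only: 4.17 − 5.00 = −0.83.
- Missing at baseline only: 5.00 − 4.17 = +0.83.
- Same domain missing at both: 4.17 − 4.17 = 0. For a participant who does change, both totals are scaled by 5/6, so the change is 5/6 of the change in the available-domain mean.

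**7. Effect on an arm mean, one affected participant of 22.** (m/6)/22 gives 0.50/22 = 0.02 at m = 3, 0.83/22 = 0.04 at m = 5, and 1.00/22 = 0.05 at m = 6.

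**The case against.** The best defence is that the formulas are a template for complete data. The SAP says before listing them that their denominators will change when items are missing, so the constants are not meant literally. The documents name no software and do not say that the line will be run verbatim. The sentence that withholds calculation does not say what *it* is. If *it* covers the total, or if a sum containing an uncalculated domain is itself taken as not calculable, the total is missing and there is no bias. The ban on imputation points the same way.

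This stands in part: the bias is conditional on how the line is executed. It does not remove the gap. The adjustment mentions items only, the rule in words also divides by all the domains, and nothing says what happens to the total. The same answers could give 4.17, 5.00 or a missing value at m = 5, and the text does not settle which.

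Two stronger readings are tempting. A reader might infer that the total is certain to be one-sixth too low; that needs SUM to skip missing domains, which the SAP does not state. A reader might also infer that the error would look like a worsening. The documents do not give the scale direction, and the sign of the error depends on the visit at which the domain is missing.

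It is also fair that losing a domain takes several skipped items within that domain, that paper is only a fallback, and that no rate of missing items is given.

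**Conclusion.** The point holds as a conditional defect in the scoring rule. The fixed divisor, combined with an adjustment confined to items, can return a wrong value for a named endpoint, and that value would conflict with the plan's own bar on imputation. The size rests on the two assumptions stated above, about SUM and about the level of the domain means. One affected participant is also an illustration and not a forecast.

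The practical impact is small. The total CLDQ score is an exploratory endpoint summarised descriptively, the study has no formal hypothesis tests (Protocol section 9.1; SAP section 3.3.4), and no key endpoint is touched.

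**What to change.** In SAP section 4.2.11.2:

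1. State that the half-or-more rule applies to the domain score.
2. Replace the fixed six by one explicit rule for the total: either the sum of the calculated domains divided by the number calculated, with a stated minimum number of domains, or a total set to missing when any domain is not calculated.

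Either choice removes the shortfall. The first keeps more participants but can compare different sets of domains at the two visits. With the unequal means used above, the five-domain mean ranges from 2.8% below (4.70) to 3.4% above (5.00) the six-domain mean of 4.83. The second avoids that and loses those totals.

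The cost is one sentence of SAP text and one line of code, with no change to data collection. It should be settled before unblinding.

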4.2.11.3 Handling of Dropouts and Missing Data

No imputation will be done.

4.2.11.4 Primary Analysis of Exploratory objective

Data will be descriptive summarized for each treatment group. PGIS will be presented with number and percentage per response category and timepoint, as well as shift from baseline. For the CLDQ and SF-36v2 actual score and change from baseline will be summarised for the different components.

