9.4.4.3 Exploratory PRO Endpoints

Results for patient-reported outcomes will be summarized by treatment group for FAS.

Further details on this will be provided in the SAP.

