Exploratory objective 6: To evaluate the effect of zibotentan/dapagliflozin and zibotentan monotherapy versus placebo on fatigue, abdominal symptoms, physical functioning and health-related quality of life					
Primary analysis	Change from baseline to Week 6 in CLDQ Fatigue and Abdominal Symptoms scores, SF-36v2 Physical Functioning score, Total CLDQ score, SF-36v2 Physical Component Summary score, SF-36v2 Mental Component Summary score, Patient Global Impression of Severity - Liver Disease	Estimand population: See above for respective arms. Analysis set: FAS	Treatment policy strategy	Descriptive statistics	4.2.11
Exploratory objective 7: To collect and store plasma, serum and urine samples for exploratory research aimed at exploring biomarkers involved in PK, PD, safety and tolerability related to zibotentan and dapagliflozin in combination versus placebo or CC1					
This objective will not be reported in the CSR.					
-	Evaluation of changes in blood and urine biomarkers	-	-	-	-

a See section [3.3.1.5](#) for details.

For timing of data collection for above endpoints please see SoA in CSP.

Unless otherwise stated the analyses within each section below will be applied for the treatment groups as indicated in the objectives. In general for comparisons of key objectives the following comparisons will be made: zibotentan/dapagliflozin versus zibotentan monotherapy, zibotentan/dapagliflozin versus placebo and zibotentan monotherapy versus placebo.

In case of convergence issues for the analysis model the **CCI** [REDACTED], defined as **CCI** [REDACTED], will be adjusted appropriately to accommodate convergence for the model.

Assessed values of the form ‘<x’ (below the lower limit of quantification) will be imputed as ‘x’ in calculations for key and exploratory objectives.

Subgroup analyses defined in sections below will be done if adequate numbers of observations are available.

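### Exploratory objective 6 asks for the effect of each active regimen versus placebo on patient-reported outcomes, but no between-arm estimate or interval is pre-specified for them

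*SAP*

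**What the plan says.** Protocol Section 3 (Table 3) and SAP 4.2 (Table 7) state the same objective: "To evaluate the effect of zibotentan/dapagliflozin and zibotentan monotherapy versus placebo on fatigue, abdominal symptoms, physical functioning and health-related quality of life". Six scores are named for it as change from baseline to Week 6: CLDQ Fatigue, CLDQ Abdominal Symptoms, CLDQ Total, SF-36v2 Physical Functioning, and the SF-36v2 Physical and Mental Component Summaries. PGIS is listed as well.

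For this objective Table 7 gives the population-level summary as "Descriptive statistics". SAP 4.2.11.4 follows suit: "Data will be descriptive summarized for each treatment group". It then specifies the content. For the severity item, "PGIS will be presented with number and percentage per response category and timepoint, as well as shift from baseline". For the scales, "For the CLDQ and SF-36v2 actual score and change from baseline will be summarised for the different components". Protocol 9.4.4.3 is equally brief: "Results for patient-reported outcomes will be summarized by treatment group for FAS". SAP 4.2.11.5 leaves room for further analyses but names no endpoint, model or contrast.

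**The concern.** The objective names a contrast with placebo, and an estimand for it needs a population-level summary that is a contrast. Here the summary is a set of per-arm descriptions, so the plan does not say what number answers the objective or how uncertain that number is.

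The study's lack of formal testing does not account for this. Exploratory objectives 2 to 5 fall under the same rule, and Table 7 gives each of them a mean difference between groups. For eGFR, for example, SAP 4.2.10.4 says: "The analysis is performed using MMRM, similar to key objectives, for absolute change from baseline".

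Two things are at stake. Any between-arm PRO result in the report would not be pre-specified. And the simplest difference a reader can build from the tables is less precise than one that adjusts for the baseline scores already being collected.

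**Working it through.** **Text check.** Six exploratory objectives are reported in the CSR. Objective 7 is not.

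| Exploratory objective | Worded against a comparator? | Table 7 summary | Method in SAP |
|---|---|---|---|
| 1 (PK) | No, characterises exposure | Descriptive | Descriptive (4.2.6.4) |
| 2 (redacted measure) | Yes | Between-group mean difference | ANCOVA (4.2.7.4) |
| 3 (AST, ALT, MELD) | Yes | Between-group mean difference | MMRM (4.2.8.4) |
| 4 (blood biomarkers) | Yes | Between-group mean difference | MMRM (4.2.9.4) |
| 5 (eGFR) | Yes | Between-group mean difference | MMRM (4.2.10.4) |
| 6 (PROs) | Yes | Descriptive | Descriptive (4.2.11.4) |

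Five objectives ask for a comparison. Four have a contrast and a model; objective 6 has neither. The list of pairwise comparisons that follows Table 7 is limited to the key objectives, so it does not fill the gap.

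**Precision check.** The plan has no PRO figure to reproduce: no SD, correlation, effect size or power is given.

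Inputs from the documents: 22 randomised per arm (Protocol 9.2) and two-sided 90% intervals (SAP 3.3).

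Assumptions: all 22 evaluable, equal score SD at baseline and Week 6, and a baseline-to-Week 6 correlation r of 0.3, 0.5 or 0.7. Results are in units of the score SD.

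- Unadjusted difference in mean change: half-width = t(0.95, 42) × √(2/22) × √(2(1 − r)). Here t = 1.682 and √(2/22) = 0.3015, with product 0.507.
- ANCOVA with baseline: half-width = t(0.95, 41) × √(2/22) × √(1 − r²). Here t = 1.683, and the product before the last factor is again 0.507.
- Chance baseline imbalance widens the ANCOVA interval by about √(1 + 1/(2n − 4)) = √(1 + 1/40) = 1.012 with n = 22.

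| r | Unadjusted | ANCOVA | ANCOVA with imbalance allowance | Narrower by |
|---|---|---|---|---|
| 0.3 | 0.507 × 1.183 = 0.600 | 0.507 × 0.954 = 0.484 | 0.490 | 18% |
| 0.5 | 0.507 × 1.000 = 0.507 | 0.507 × 0.866 = 0.439 | 0.445 | 12% |
| 0.7 | 0.507 × 0.775 = 0.393 | 0.507 × 0.714 = 0.362 | 0.367 | 7% |

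A simulation of 40,000 two-arm trials per setting gave mean half-widths of 0.60, 0.50 and 0.39 SD unadjusted and 0.49, 0.44 and 0.36 SD adjusted, with the same percentage reductions.

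If only 18 per arm were evaluable (also an assumption), the same formulas without the imbalance allowance give 0.67, 0.56 and 0.44 SD unadjusted and 0.54, 0.49 and 0.40 SD adjusted.

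**The case against.** The best defence is that the descriptive treatment is consistent and probably intended. Protocol 9.4.4.3, SAP Table 7 and SAP 4.2.11.4 all agree on it. The safety objective in SAP 4.6 is also worded against placebo and is also summarised descriptively by arm, so objective 6 is not the only case in this SAP. These points stand, and they keep the matter minor. They do not remove the mismatch within the exploratory set, where every other objective worded as a comparison receives an estimate of one.

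A reader might infer that the arms are never compared and that the objective cannot be answered. The documents do not support that. The summaries are by randomised arm, placebo included, and SAP 3.3 supplies n, mean and SD. A change common to all arms would show in the placebo column, and subtracting mean changes gives a valid, if unadjusted, randomised contrast for the CLDQ and SF-36v2 scores.

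A reader might also fear that each arm's change will be declared significant by itself. SAP 4.2.11.4 plans no within-arm PRO interval or test, so such a false-signal rate would describe an output that is not planned.

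Nor does SAP 4.2.11.5 say that further analyses would be chosen after the data are seen. It gives no timing. The fair statement is that none is pre-specified.

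**Conclusion.** The point holds in a limited form. The objective calls for two contrasts with placebo, and the plan pre-specifies neither an estimate nor an interval for them. What can be recovered from the tables is an unadjusted difference.

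Adjusting for baseline would narrow the 90% interval by 7% to 18%. That range rests on the assumed correlations of 0.3 to 0.7, equal SDs and 22 evaluable per arm, none of which the documents give for the PROs. The gain is smallest when the correlation is high. Even the adjusted interval remains wide, at roughly a third to a half of an SD either side, so the result would still be exploratory.

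It might seem natural to extend this to a between-arm risk difference for PGIS worsening. The protocol does not support that: Section 3 lists PGIS at baseline and Week 6, and the summary of changes explains that it was separated because it is not evaluated as a change. PGIS should stay descriptive.

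**What to change.** In SAP 4.2.11.4, for the six named scores (CLDQ Fatigue, CLDQ Abdominal Symptoms, CLDQ Total, SF-36v2 Physical Functioning, PCS and MCS), add an ANCOVA of Week 6 change from baseline with treatment and the baseline score as terms. Report the LS mean difference and 90% CI for zibotentan/dapagliflozin versus placebo and for zibotentan versus placebo. PROs are collected once at baseline and once at Week 6, so ANCOVA suits them; SAP 4.2.7.4 already uses it for another measure with one baseline and one post-baseline assessment.

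In Table 7, change the population-level summary for these six scores to the between-group mean difference used for exploratory objectives 2 to 5. Leave PGIS and the remaining domain scores descriptive.

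The cost is SAP wording and a few tables, with no new data, visits or participants. It adds 6 × 2 = 12 exploratory intervals without multiplicity adjustment, as the plan already accepts elsewhere. If the sponsor does want description only, rewording objective 6 and its estimand accordingly would also remove the mismatch, but would leave the versus-placebo question without an estimate.

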4.2.11.5 Additional Analyses of the Exploratory objective

Additional analyses may be conducted as appropriate.

4.2.11.6 Subgroup Analyses

Not applicable.

